Molecular Subtyping of Extensive Stage Small Cell Lung
Cancer and Relevant Clinical Significance
(The MOSAIC study)

2022.3.29

Version 1.0

Objective:

- (1) Validating the predictive value of transcriptome-based molecular subtyping of extensive stage small cell lung cancer(SCLC) for the efficacy of PD-1/PD-L1 inhibitor in the first line setting.
- (2) Exploring the differences of immune microenvironment between different SCLC subtypes to reveal the mechanisms of immunotherapy resistance of SCLC

Protocol:**1.1 Design**

This study is a retrospective observational study without intervention in clinical treatment. In prior study, the transcriptomic data was used to classify SCLC into four subtypes, which might have different sensitivity to immunotherapy. Therefore, molecular subtyping could be used as an important biomarker for predicting efficacy of immunotherapy, which need further validation. This study will explore the predictive value of different subtypes of SCLC for immunotherapy and mechanisms of immunotherapy resistance of SCLC. Extensive stage SCLC patients receiving first-line standard treatment will be enrolled in this study. Baseline tumor tissue samples and peripheral blood samples will collected for transcriptome and immunohistochemistry analysis etc. Based on these results, patient will be classified into four subtypes and efficacy and safety of treatment will be recorded. We will compare the efficacy between different subtypes of SCLC and analyze whether molecular typing could predict the efficacy of immunotherapy; Compare the differences in immune microenvironment of different subtypes of SCLC to reveal the mechanism of immunotherapy resistance. The treatment regimen involved in this study follows guidelines for the first-line treatment of extensive stage SCLC: cisplatin+etoposide or carboplatin+etoposide with or without approved PD-(L)1 inhibitor for SCLC. Treatment options are determined by the patient's supervising physician.

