1.3 Endpoint and follow up

Primary endpoint: Progression-free survival

Secondary endpoint: Overall survival; Objective response rate; molecular subtyping and tumor microenvironment biomarkers.

Follow-up plan:

- 1) Patients will be reviewed every 2 cycles during treatment to assess effectiveness and record vital signs and test results.
- 2) Patients will be reviewed periodically every 3 months after completion of treatment until disease progression.
- 3) After disease progression, patients will continue to be followed up every 3 months to record post treatment until die or lost follow-up.

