1.5 Statistics

All measurements will be expressed as mean \pm standard deviation. COX regression analysis was used to examine the correlation between immune indicators and efficacy, and one-way ANOVA will be used to analyze the correlation between the variables and the efficacy of immunotherapy or adverse effects. The number of different cell types will be compared between patient subgroups using the Wilcoxon rank-sum and Jonckheere-Terpstra tests. Differences between the two groups will be analyzed using a two-sided t-test. Categorical variables and continuous variables will be calculated according to frequency counts and median values respectively. The statistical analysis software is GraphPad Prism and SPSS 19.0. $P < 0.05$ will be considered statistically different.

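### Objective 1 claims validation of subtype as a predictor of PD-(L)1 efficacy, but no subtype, direction, contrast or success criterion is fixed

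*Combined protocol and SAP*

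**What the plan says.** The combined protocol and SAP gives the first objective as "Validating the predictive value of transcriptome-based molecular subtyping of extensive stage small cell lung cancer(SCLC) for the efficacy of PD-1/PD-L1 inhibitor" in first-line treatment. The second objective is worded separately as exploration.

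Section 1.1 gives the background: in prior work "the transcriptomic data was used to classify SCLC into four subtypes, which might have different sensitivity to immunotherapy". It says this needs further validation, then describes the present aim differently: "This study will explore the predictive value of different subtypes of SCLC for immunotherapy". The planned comparison is one sentence: "We will compare the efficacy between different subtypes of SCLC and analyze whether molecular typing could predict the efficacy of immunotherapy". Treatment, chemotherapy with or without a PD-(L)1 inhibitor, is chosen by the treating physician.

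Section 1.3 fixes the endpoint: "Primary endpoint: Progression-free survival". Section 1.4 gives 80-100 patients per treatment group with no rationale.

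Section 1.5 assigns Cox regression to immune indicators. It also lists ANOVA, rank tests and a two-sided t-test, and says that P<0.05 "will be considered statistically different". It names no model containing treatment, subtype and their interaction, and no multiplicity rule. Nowhere does the document name the four subtypes or say which should benefit.

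**The concern.** Validation needs a claim that can fail. With four subtypes and no stated contrast, an analyst can compare each subtype with the rest (four ways), split them two against two (three ways) or compare pairs (six ways), in either direction. Nothing in the plan says which of these decides Objective (1). The study is retrospective, so outcomes may already be on file when the choice is made.

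Two things are at stake. A chance separation found by searching could be reported as validation of a predictive biomarker. Also, a comparison of subtypes that does not involve treatment effect could show a purely prognostic difference and be read as predictive.

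**Working it through.** **The plan's own figure.** The 80-100 per group in 1.4 cannot be reproduced, because no power, effect size, event count or subtype prevalence is given. It serves here only as an input: 160-200 patients in total.

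**Assumptions, not from the documents.** 90% of patients have a PFS event; the treatment groups are equal in size within each subtype; subtype shares are equal (25% each) or 45/25/20/10%; tests are two-sided at 0.05.

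**Model.** The PD-(L)1-versus-chemotherapy log hazard ratio in subtype *i* is approximately normal with variance 4/*e*ᵢ, where *e*ᵢ is the number of events in that subtype. A contrast of subtype set A against set B is the difference of the inverse-variance-weighted means, divided by its standard error.

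**False positives with no true effect modification** (200,000 simulated draws):

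| What is tested on PFS | P(at least one P<0.05) | If the tests were independent |
|---|---|---|
| One fixed contrast | 5% | 5% |
| One global 3-df interaction test | 5% | 5% |
| Four one-versus-rest contrasts | about 17% | 1 − 0.95⁴ = 18.5% |
| Six pairs | about 20% | 1 − 0.95⁶ = 26.5% |
| All seven splits | about 21% | 1 − 0.95⁷ = 30.2% |

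The simulated rates lie below the independence figures because the contrasts share patients. They hardly change with subtype shares or with a total of 160 or 200.

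**Power of a named contrast against the global test.** Take equal subtypes, one with HR 0.35 and the others 0.85, and 160 patients:

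- Events: 0.9 × 160 = 144, so 36 in the named subtype and 108 in the rest.
- Variance of the contrast: 4/36 + 4/108 = 0.148, so SE = 0.385.
- Log ratio: ln(0.35/0.85) = −0.887.
- Power: Φ(0.887/0.385 − 1.96) = Φ(0.345) ≈ 63%.

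Now suppose two of the four subtypes have HR 0.35 and only one of them is named. The contrast shrinks to 0.887 × 2/3 = 0.592, and power is Φ(0.592/0.385 − 1.96) = Φ(−0.42) ≈ 34%.

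| Assumed pattern (160 to 200 patients) | Named one-versus-rest, 1 df | Global, 3 df |
|---|---|---|
| One subtype 0.35, others 0.85; equal shares | 63% to 73% | 46% to 56% |
| Same HRs, 45/25/20/10% split, the 20% subtype sensitive | 57% to 66% | 40% to 49% |
| Two of four equal subtypes 0.35, only one named | 34% to 40% | 59% to 70% |
| Graded HRs 1.0/0.85/0.7/0.5 on the 45/25/20/10% split, best named | 18% to 21% | 17% to 20% |

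The named contrast gains in the first two patterns, loses in the third and is nearly level in the fourth.

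**What the sample size can detect.** For a single contrast with a subtype share of 10-25% and 80-100% events, the interaction HR ratio detectable with 80% power is about 0.19 to 0.40. At the favourable end (100 per group, 25% share, all with events), the variance is 2/25 + 2/75 = 0.107 and SE = 0.327, so the ratio is exp(−2.80 × 0.327) = 0.40.

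**The case against.** The strongest reply is that the planned sentence, "We will compare the efficacy between different subtypes of SCLC", fits a single four-group comparison as well as it fits a search. One global interaction test holds its error at 5% and is a legitimate test of whether the classification predicts efficacy. This stands: the 17-21% is not a property of the plan as written. It applies only if several contrasts are run unadjusted and any hit is reported. However, the plan does not specify a global test either.

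A second reply is that the study is exploratory, as 1.1 partly says. That softens the claim but does not settle it. Objective (1) says validation, Objective (2) is separately worded as exploration, and the two descriptions of the first aim conflict.

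A third is that PFS is named as primary. That limits the choice of endpoint, but not of subtype, direction or contrast.

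A reader might go further and infer that any pattern with P<0.05, even one opposite to the prior study, would count as validation under this plan. The documents do not say so. Section 1.5 states a general significance convention, and no passage ties it to Objective (1). What the text supports is that no success criterion is given. Nor do the documents show that the prior study singled out one sensitive subtype, so a remedy cannot take that for granted.

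**Conclusion.** The concern holds in a limited form. Objective (1) is worded as validation, yet the plan fixes no subtype, direction, contrast, interaction test or success criterion, and elsewhere calls the same aim exploratory. If subtype contrasts on PFS are tested one by one without adjustment, the chance of a false positive is about 17% to 21%, against 5% for one fixed test. Those rates assume no true effect modification and the normal approximation, and they depend little on the assumed subtype shares.

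It might be inferred that naming one subtype always gives more power. It does not: the gain depends on the assumed pattern of hazard ratios, so it should not be given as a general benefit. The case for fixing one test rests on error control and on having a claim that can fail. Even then, only a large interaction is detectable with 80-100 per group under the assumptions shown.

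**What to change.** Before subtype and outcome data are merged, state in 1.1 and 1.5 that Objective (1) rests on one treatment-by-subtype interaction test on PFS. Use a Cox model adjusted for listed baseline prognostic factors, because physicians choose the treatment. Adjustment deals only with measured factors, so a significant interaction would still need cautious reading.

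- If the prior study singled out a sensitive subtype or group of subtypes, name it and the expected direction. Use the 1-df contrast of that subtype or group against the rest, and require two-sided P<0.05 in that direction. With no true effect modification, this succeeds by chance about 2.5% of the time.
- Otherwise, use the 3-df global interaction test at 0.05.
- Report the four subtype-specific hazard ratios with 95% confidence intervals as descriptive.
- If no such test is fixed beforehand, reword Objective (1) as exploratory, in line with 1.1.

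The cost is a few sentences, with no new patients or assays. Signals in other subtypes become hypothesis-generating only, and the 1-df contrast has less power than the global test if the sensitive subtypes are misnamed.

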1.2 Patients**Inclusion Criteria:**

- 1) Male or female, aged 18 to 100 years
- 2) Patients with untreated advanced small cell lung cancer clearly diagnosed by histopathology
- 3) Be able to provide tumor biopsy tissue sample for molecular analysis
- 4) ECOG score: 0 ~2;
- 5) Expected survival of more than 3 months.
- 6) Has at least 1 measurable or evaluable tumor lesion with a longest diameter ≥ 10 mm at baseline (in case of lymph nodes, a shortest diameter ≥ 15 mm is required) according to RECIST v1.1
- 7) Received first-line chemotherapy or chemotherapy + PD-(L)1 inhibitor and be able to provide complete treatment information and efficacy evaluation results.
- 8) Voluntary signed informed consent and expected good compliance.

Exclusion Criteria:

- 1) Patient unable to tolerate chemotherapy.
- 2) Patients unable to provide tumor tissue samples for testing
- 3) Patients with other malignant tumors or a history of other malignant tumors
- 4) Patients have any other reason to be unfit to participate in this study.

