1.4 Sample Size

Chemotherapy: 80-100 cases.

Immunotherapy+chemotherapy: 80-100 cases.

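### Objective (1) asks whether subtype predicts PD-(L)1 efficacy, but Section 1.5 names no analysis with treatment and subtype together, so a prognostic difference could be reported as predictive

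*Combined protocol and SAP*

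**What the plan says.** Objective (1) begins "Validating the predictive value of transcriptome-based molecular subtyping", with the efficacy of first-line PD-(L)1 inhibition as the target. Section 1.1 gives the premise, that earlier transcriptomic work could "classify SCLC into four subtypes, which might have different sensitivity to immunotherapy". It then states the plan: "We will compare the efficacy between different subtypes of SCLC and analyze whether molecular typing could predict the efficacy of immunotherapy". The same section also uses a softer verb: "This study will explore the predictive value of different subtypes of SCLC for immunotherapy".

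Both treatments are represented. Section 1.2 admits patients who "Received first-line chemotherapy or chemotherapy + PD-(L)1 inhibitor", and Section 1.4 plans "Chemotherapy: 80-100 cases" and the same number on the combination. Treatment is not randomised: "Treatment options are determined by the patient's supervising physician" (1.1). Section 1.3 gives "Primary endpoint: Progression-free survival".

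Section 1.5, the only statistics section, lists:
- Cox regression relating immune indicators to efficacy, with no other terms named;
- one-way ANOVA relating unnamed variables to immunotherapy efficacy or adverse effects;
- rank tests on cell numbers between patient subgroups;
- a two-sided t-test between two groups that are not defined.

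**The concern.** A subtype is predictive if the effect of adding PD-(L)1 to chemotherapy differs between subtypes. It is prognostic if its patients do better or worse whichever treatment they receive. A subtype with a milder natural course has longer PFS in both treatment groups, so comparing subtypes among PD-(L)1 patients alone will tend to show a difference even when every subtype gains equally from PD-(L)1.

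Running the comparison separately in each treatment group does not settle the matter. A significant result with PD-(L)1 and a non-significant one with chemotherapy is not a test of whether the two differ.

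At stake is the study's first objective, on its primary endpoint. A prognostic difference labelled predictive would mislead readers about which patients benefit from PD-(L)1.

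**Working it through.** **Step 1. Which named analysis could separate the two?** Separation needs treatment and subtype in one analysis.

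| Analysis in 1.5 | Tied to | Treatment and subtype together? |
|---|---|---|
| Cox | immune indicators and efficacy | neither is named as a term |
| One-way ANOVA | immunotherapy efficacy or adverse effects | no; it has a single factor |
| Rank tests | cell numbers | not an efficacy analysis |
| t-test | two undefined groups | no; single factor whichever groups are meant |

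The second half of the Section 1.1 sentence restates the objective without naming a contrast, a model or a criterion.

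**Step 2. How often could a prognostic subtype look predictive?** The plan has no figure of its own to reproduce: Section 1.4 gives a range without effect size, power or event count. From the plan come four subtypes, 80-100 per group and alpha 0.05. The rest is assumed: equal subtype shares, 85% PFS events, one purely prognostic subtype and zero interaction.

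Events per group: d = 0.85 × 80 = 68, or 0.85 × 100 = 85.

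For the 3-df between-subtype test within one group, the approximate non-centrality is λ = d × 0.25 × 0.75 × (ln HR)². At HR 0.6 and d = 68, λ = 68 × 0.1875 × 0.261 = 3.33. The chance p of significance is the upper tail of a non-central chi-square (3 df) beyond 7.81. If both groups are tested separately and share this p, the chance of significance with PD-(L)1 but not with chemotherapy is p(1 − p).

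Simulation used exponential PFS, treatment HR 0.75, random subtype counts and likelihood-ratio tests, with 500 to 1,500 runs per scenario.

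| Prognostic HR | λ | p, formula | p, simulated | p(1 − p), formula | Discordant, simulated |
|---|---|---|---|---|---|
| 0.8 | 0.63-0.79 | 9-10% | about 10% | 8-9% | about 8-10% |
| 0.7 | 1.62-2.03 | 16-19% | 13-18% | 14-16% | 10-15% |
| 0.6 | 3.33-4.16 | 30-37% | 27-37% | 21-23% | 18-25% |
| 0.5 | 6.13-7.66 | 53-63% | 48-60% | 23-25% | 20-25% |

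With 500 runs, the Monte Carlo standard error at 50% is √(0.5 × 0.5/500) = 2.2 points, so the simulated ranges are good to a few points. In the same simulations the 3-df interaction test rejected in about 5-7%, close to nominal.

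**Step 3. How precise would the interaction analysis be?** For one deviating subtype with a 25% share, SE² of the log ratio of HRs is 2/(0.1875 d). At a ratio of 0.5, λ = (ln 0.5)² × 0.1875 d/2 = 3.06 (n = 80) or 3.83 (n = 100), giving power of 28% or 34%. Simulation gives about 27-35%.

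For the treatment HR within a subtype:
- 25% share: 17-21 events per treatment-by-subtype cell. √(2/17) = 0.34 and √(2/21.25) = 0.31. The simulated median SEs are slightly larger, 0.36 and 0.32, so the 95% CI factor exp(1.96 × SE) is roughly ×/÷ 1.85-2.0.
- 15% share: 0.15 × 68 = 10.2 to 0.15 × 85 = 12.75 events per cell. SE is 0.44-0.40, and the factor is about ×/÷ 2.2-2.4.

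**The case against.** The strongest reply is that Section 1.1 declares an intent to analyse prediction, and that enrolling a chemotherapy group in the same numbers suggests a control was meant. Section 1.5 leaves the Cox covariates and the t-test groups open, so the right model could be fitted without departing from the text. This stands in part. A reader might infer that the plan overlooks prediction, or rules out a joint analysis. The documents support neither: the intent is stated and the method is missing.

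A reader might also take the percentages as the plan's false-positive rate. They are not. Nowhere does the plan say that subtypes will be compared by PFS within the PD-(L)1 group only, or in each group separately. A significant result there also detects a real prognostic effect; it becomes an error only when called predictive. The size depends on that effect, which the documents do not give. At HR 0.8 the within-group figure is about 10%.

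Finally, the study is retrospective and Section 1.1 speaks of exploring, while the proposed test has low power. That is a reason for modest claims. It does not justify a contrast that answers another question, and Objective (1) speaks of validating.

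**Conclusion.** The point holds as an omission. Objective (1) is a claim about how the PD-(L)1 effect varies by subtype, and no analysis named in Section 1.5 estimates or tests that. Nor does the plan say how the chemotherapy group will be used, or what result would count as predictive. A prognostic difference could therefore be presented as predictive while following the plan as written.

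This conclusion rests on the text alone. Its numerical size is illustrative and depends on the assumed subtype shares, event fraction and prognostic HR: small for a weakly prognostic subtype, and near one study in two for a strongly prognostic one. It would be going too far to say that adding the interaction model turns this study into a validation. At 80-100 per group it does not.

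**What to change.** In Section 1.5, specify for Objective (1):

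1. A Cox model for PFS with treatment, four-level subtype, their interaction, and a short prespecified list of baseline covariates that includes age and ECOG. Adjustment is needed because the physician chooses treatment; both variables are already known from the eligibility criteria.
2. A 3-df likelihood-ratio test of the interaction, since the documents name no subtype in advance.
3. Reporting of the treatment HR with 95% CI within each subtype, and of the ratios of HRs.
4. Wording rules: predictive only for the interaction; prognostic for subtype differences within one treatment group; a non-significant interaction reported as an estimate with its CI, not as evidence of no prediction.

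The cost is plan wording and one model on data already being collected. The model has 7 treatment and subtype terms (1 + 3 + 3) plus 2-3 covariate terms. At 85% events, 160-200 patients give 136-170 events, so 136/10 to 170/9, about 14-19 events per parameter.

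The downside is the low precision shown above. By simulation under the same assumptions, 80% power at a ratio of HRs of 0.5 would need about 310-320 patients per group with the 3-df test. Unmeasured confounding also remains, because treatment was not randomised.

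### Objective 2 compares immune features between subtypes with no rule separating the features that define a subtype from the features that are tested

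*Combined protocol and SAP*

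**What the plan says.** Section 1.1 sets out the sequence. On the assays: "Baseline tumor tissue samples and peripheral blood samples will collected for transcriptome and immunohistochemistry analysis etc". On the grouping: "Based on these results, patient will be classified into four subtypes and efficacy and safety of treatment will be recorded". The comparison between those groups then follows: "Compare the differences in immune microenvironment of different subtypes of SCLC to reveal the mechanism of immunotherapy resistance". Objective (2) states the same aim: "Exploring the differences of immune microenvironment between different SCLC subtypes to reveal the mechanisms of immunotherapy resistance of SCLC".

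The basis of the subtype call is described in two ways. The sentence on grouping in section 1.1 points back to both assays. Objective (1) mentions the transcriptome alone: "Validating the predictive value of transcriptome-based molecular subtyping of extensive stage small cell lung cancer(SCLC". Section 1.1 also traces the scheme to earlier work: "In prior study, the transcriptomic data was used to classify SCLC into four subtypes". No gene list, centroid set or algorithm is given.

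Section 1.5 supplies the tests: "The number of different cell types will be compared between patient subgroups using the Wilcoxon rank-sum and Jonckheere-Terpstra tests". It does not name the assay that yields the cell numbers. Its general rule is that P<0.05 "will be considered statistically different". Section 1.3 lists microenvironment biomarkers, together with molecular subtyping, among the secondary endpoints.

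**The concern.** A rank test has its nominal 5% error rate when the groups were formed without the variable under test. If a gene or protein marker helped decide a patient's subtype, its distribution is pushed apart between subtypes even when there is no biology behind it. The same holds, more weakly, for an immune score that contains some classifier genes or shares measurement noise with them.

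The plan allows this and gives a reader no means of detecting it. A difference that only restates how the subtypes were drawn could be reported beside genuine differences, under the same threshold, as a mechanism of immunotherapy resistance. Changing the test, adjusting for multiplicity or enlarging the sample would not cure it.

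**Working it through.** The plan gives no figure to reproduce here. The check is whether the mechanism operates at the planned size, and how strongly.

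**Inputs from the documents.** Section 1.4: 80–100 patients per treatment group, so 80+80 = 160 to 100+100 = 200 in total. Section 1.1: four subtypes. Section 1.5: threshold 0.05.

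**Assumptions.** The number of defining features, the correlations and the assay reliability are not in the documents, so ranges are used. All features are simulated as standard normal with no true subtypes.

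**Step 1. Rejection rates for defining features** (Kruskal–Wallis across four groups; ranges cover n = 160 and n = 200). Two separate sets of simulations were run. The 10-, 50- and 200-feature rows are one set, and the rest are the other.

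| How groups are formed | Defining features | Defining features, P<0.05 | Independent features, P<0.05 |
|---|---|---|---|
| Clustering this cohort | 8 | 93–95% | 4.3–4.5% |
| Clustering this cohort | 10 | 91–93% | 4–5% |
| Clustering this cohort | 20 | 79–83% | 4.8–5.5% |
| Clustering this cohort | 50 | 57–63% | 4–5% |
| Clustering this cohort | 100 | 36–42% | 4.5–5.0% |
| Clustering this cohort | 200 | 21–25% | 4–5% |
| Fixed nearest-centroid rule | 8 | about 100% | 5.8–6.0% |
| Fixed nearest-centroid rule | 20 | 82–90% | 2.8–4.3% |
| Fixed nearest-centroid rule | 100 | 20–24% | 4.5–5.0% |

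The fixed-rule rows matter because section 1.1 takes the four subtypes from an earlier study. Fixing the classifier in advance does not remove the effect. The effect weakens as the number of defining features grows.

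**Step 2. A test that the plan names.** Section 1.5 does not name Kruskal–Wallis. A Wilcoxon rank-sum test of one defining feature, one subtype against the rest, rejects in 16–65% of runs under clustering and 36–100% under the fixed rule. Jonckheere–Terpstra was not simulated.

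**Step 3. Partial overlap.** Suppose subtype is the largest of four independent scores, and an immune readout correlates with one score only through shared genes or noise. Correlations of 0.2, 0.3 and 0.5 give P<0.05 in 19–24%, 43–53% and 91–96% of runs.

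**Step 4. Size of the built-in gap, by hand.** Under the same largest-of-four rule, the expected maximum of four independent standard normals is 1.03. A score has overall mean zero and wins in a quarter of patients, so its mean in the other three groups is −1.03/3 = −0.34. The gap is 1.03 + 0.34 = 1.37 SD under full overlap. An independent reading of the same feature would show this gap multiplied by the reliability of the RNA reading. At an assumed 0.5 to 0.9 that is 1.37×0.5 = 0.69 SD to about 1.24 SD. Reusing one reading for both grouping and testing therefore also exaggerates real differences.

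**Step 5. Does dropping the defining features suffice?** In the second set, a feature outside the panel but correlated 0.5 with one defining feature rejects in these proportions:

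- 8 features: 62–74%
- 20 features: 25–41%
- 100 features: 8–19%

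The lowest value, 7.5% of 200 runs, is within simulation error of 5% (standard error √(0.05×0.95/200) = 1.5 percentage points). The others show that removal helps but is not a complete remedy.

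**The case against.** The strongest reply is that no overlap has been demonstrated. The documents list no classifier genes, do not say that any immune feature defines a subtype, and do not say that the immune readouts come from RNA. Objective (1) and the reference to earlier work both point to a transcriptome-only call. The cell numbers in section 1.5 could well be IHC counts of markers outside the classifier, and their P-values would not carry this built-in difference. The assay list is also open-ended and peripheral blood is collected, so another data source may exist.

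Most of this stands, and it limits the point. A reader might infer that the subtypes are in fact defined by immune features, or that every microenvironment P-value in the study is meaningless. The documents support neither. Nor do defining features always reach significance: at 200 features only 21–25% of tests do. With a classifier fixed in advance, a test on a defining feature correctly rejects a null that is false. The error lies in presenting that built-in difference as a discovery or a mechanism.

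Two further limits are fair. The clustering results describe subtypes found afresh in this cohort, which is not the obvious reading of a validation objective. And a correlation of 0.2 to 0.5 could reflect real biology as easily as shared genes or noise.

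What the reply does not answer is the missing rule. As written, the plan permits the circular comparison, describes the basis of the call in two ways, and applies one threshold to every readout.

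**Conclusion.** The concern holds as an unguarded risk whose extent is unknown. For any immune readout that shares genes or markers with the subtype call, P<0.05 is not evidence of a discovered difference or of a resistance mechanism. Under a simulated null at the planned 160–200 patients, defining features reject in about 20–100% of Kruskal–Wallis tests, against about 5% for independent features. Those figures rest on assumed panels of 8 to 200 features and cannot be narrowed from the documents.

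The reach is limited. Objective 2 is exploratory and microenvironment biomarkers are a secondary endpoint. Primary progression-free survival is untouched, as are immune features measured separately from, and independent of, the subtype call.

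**What to change.** Amend sections 1.1 and 1.5 as follows.

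1. Reconcile section 1.1 with Objective (1) by stating that subtype is assigned from the transcriptome classifier only.
2. Remove every classifier gene from transcriptome-derived immune scores before comparing them between subtypes.
3. Show any immune feature that is part of a subtype's definition descriptively, without a P-value, and do not report it as a finding or a mechanism.
4. Where IHC immune-cell counts from markers outside the subtype call are available, use them to corroborate transcriptome-derived differences. State that removing classifier genes does not remove correlation or shared assay noise in the remaining genes.

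Item 4 is conditional because the plan names no immune IHC markers; making IHC the main readout would be a design choice. The cost of items 1 to 3 is protocol wording and one check of gene-list overlap. The downside is that fewer transcriptome immune features are tested and some apparent differences shrink.
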